Unless stated otherwise, all statistical tests will be two-sided and conducted at the 5% level, and all quoted confidence intervals will be two-sided 95% confidence intervals.

Sample Size:

A total of 160 subjects (80 in the THS 2.2 arm, 40 in the CC arm, and 40 in the SA arm) will be randomized. This sample size is needed to attain 80% power to show at least a 50% reduction for any of the primary BoExp in THS 2.2 compared to the CC arm, one-sided test with 2.5% type I error probability.

TABLE OF CONTENTS

SYNOPSIS.....	1
TABLE OF CONTENTS.....	14
LIST OF ABBREVIATIONS AND DEFINITIONS OF TERMS.....	19
1 INSTITUTIONAL REVIEW BOARD (IRB) APPROVAL	27
1.1 Institutional Review Board (IRB) Approval.....	27
1.2 Ethical Conduct of the Study	28
1.3 Subject Information and Consent.....	28
1.4 Good Clinical Practice and Regulatory Requirements	30
2 INTRODUCTION	31
2.1 Background.....	31
2.2 Purpose of the Study	34
2.3 Anticipated Benefits and Risks.....	34
3 STUDY OBJECTIVES.....	36
3.1 Primary Objective	36
3.2 Secondary Objectives.....	36
3.3 Exploratory Objectives	37
3.4 Study Endpoints	38
4 INVESTIGATIONAL PLAN.....	44
4.1 Overall Study Design and Plan.....	44
4.2 Rationale for Study Design and Control Groups	47
4.3 Appropriateness of Measurements.....	49
4.4 Study Duration	49
5 STUDY POPULATION	51
5.1 Selection of Study Population.....	51
6 INVESTIGATIONAL PRODUCTS	57

Confidentiality statement: Data and information contained in this document are considered to constitute trade secrets and confidential commercial information, and the legal protections provided to such trade secrets and confidential information are hereby claimed under the provisions of applicable law. No part of this document may be publicly disclosed without the written consent of Philip Morris Products S.A.

6.1	Description of Investigational Products.....	57
6.2	Use of Investigational Product.....	60
6.3	Method for Assigning Subjects to Study Arms	61
6.4	Blinding.....	62
6.5	Investigational Product Accountability and Compliance	62
6.6	Restrictions	64
6.7	Concomitant Medications	65
7	STUDY PROCEDURES	69
7.1	Informed Consent/Subject Information Sheet	69
7.2	Advice on the Risk of Smoking and Debriefing.....	69
7.3	Support for the Smoking Abstinence Arm.....	70
7.4	Clinical Assessments	70
7.5	Biomarker Assessment.....	75
7.6	Laboratory Assessments	79
7.7	Sampling Handling and Storage	81
7.8	Other Study Procedures	84
8	ADVERSE EVENTS.....	91
8.1	Definitions.....	91

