12.1.5 Significance Level for Inferential Analysis

Unless stated otherwise, all statistical tests will be two-sided and conducted at the 5% level, and all quoted confidence intervals (CIs) will be two-sided 95% CIs.

The primary endpoints will be tested using a multiple testing procedure to preserve the overall alpha level by simultaneously testing the endpoints using a closed procedure with each test performed at an alpha level of 5%. This implies that statistical significance is required for all primary endpoints in order to be able to make confirmatory claims about any of the endpoints.

Full details of this approach will be provided in the SAP.

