Abbreviations: 3-HPMA = 3-hydroxypropylmercapturic acid; CC = conventional cigarettes; COHb = carboxyhemoglobin; CV = coefficients of variation; MHBMA = monohydroxybutenyl mercapyuric acid; MR = mean ratios; S-PMA = S-phenylmercapturic acid; THS 2.2 = Tobacco Heating System 2.2.

Based on these two sets of assumptions, the power to demonstrate a reduction was computed. Table 18 describes the expected power to demonstrate a reduction on 4 primary BoExps in smokers switching from CC to THS 2.2 as compared to those continuing to smoke CC, using one-sided test with 2.5% type I error probability using the assumptions from YVD-CS01-EU and ZRHX-EX-01 and 160 smokers (80 in THS 2.2, 40 in CC, and 40 in the SA arm).

Confidentiality statement: Data and information contained in this document are considered to constitute trade secrets and confidential commercial information, and the legal protections provided to such trade secrets and confidential information are hereby claimed under the provisions of applicable law. No part of this document may be publicly disclosed without the written consent of Philip Morris Products S.A.

Table 18. Expected Power (YVD-CS01-EU and ZRHX-EX-01 Studies Assumptions)

Assumptions	Reduction					
	50%	51%	52%	53%	54%	55%
YVD-CS01-EU	96%	91%	85%	75%	63%	48%
ZRHX-EX-01	>99%	>99%	96%	81%	48%	16%

A total of 160 smokers (80 in THS 2.2, 40 in CC, and 40 in the SA arm) will be randomized to demonstrate a reduction of at least 50% on 4 primary BoExps in smokers switching from CC to THS 2.2 as compared to those continuing to smoke CC, using one-sided test with 2.5% type I error probability.

Power considerations related to secondary endpoints of biological changes:

The sample size is sufficient to obtain 95% CIs for the ratio between (geometrical) mean levels of primary BoExps in THS 2.2 and SA see Section 12.2 with upper and lower limits deviating not more than 18% from the point estimates, with an 80% overall probability of achieving the desired precision of estimating the true mean.

This study has 80% power using a one-sided test with 2.5% type I error probability:

- To detect a 0.631 [ml/min/kg] (29%) difference between THS 2.2 and CC in CYP1A2 activity, as measured by the CAF clearance, assuming a standard deviation of 0.564. Effect size and variability are derived from data obtained in the YVD-CS01-EU study sponsored by PMI.

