12.4 Primary Analysis

12.4.1 Primary Endpoint Analysis Variables

The primary endpoints are:

- COHb on Day 5.
- MHBMA on Day 5.

Confidentiality statement: Data and information contained in this document are considered to constitute trade secrets and confidential commercial information, and the legal protections provided to such trade secrets and confidential information are hereby claimed under the provisions of applicable law. No part of this document may be publicly disclosed without the written consent of Philip Morris Products S.A.

- 3-HPMA on Day 5.
- S-PMA on Day 5.

See section 3.4.1.

Evaluation Criterion: The study will be considered successful if the study demonstrates a 50% reduction or more for all four primary BoExp in the THS 2.2 arm compared to the CC arm (as measured on Day 5), using a one-sided test with 2.5% type I error probability.

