12.4.4 Confirmatory Analysis

The hypothesis to be tested for each of the primary and secondary biomarkers of exposure is that the geometric mean level on Day 5 of the biomarker for THS 2.2 is lower relative to CC.

Analysis of BoExp will be conducted on the natural log scale. In order to test the following hypothesis

Null hypothesis (H0): $m_1 \geq m_2$

Alternative hypothesis (H1): $m_1 < m_2$

Where m_1 and m_2 are the geometric means of the biomarker levels on Day 5 for THS 2.2 and CC respectively.

The transformed data will be analyzed by means of a generalized linear model using product arm as covariate adjusting for the following baseline information: sex, average cigarette

consumption over the previous 4 weeks, and baseline value of endpoint. Estimates of differences between groups will be back-transformed to provide relative effects.

Assumptions of the analysis of variance model will be tested. Markedly non-lognormally distributed BoExp data will be transformed or analyzed by appropriate non-parametric methods.

Should more than 20% of the subjects be excluded from the FAS, would the above confirmatory analysis will be repeated on the PP population.

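### The synopsis sizes the trial on 80% power for any primary biomarker, while the protocol's own calculation gives 96% or more for all four at the same sample size

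*Protocol*

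**What the plan says.** The Sample Size paragraph of the protocol synopsis gives the allocation ("80 in the THS 2.2 arm, 40 in the CC arm, and 40 in the SA arm") and then the justification: "This sample size is needed to attain 80% power to show at least a 50% reduction for any of the primary BoExp", for a "one-sided test with 2.5% type I error probability".

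Protocol section 12.2 does the calculation. Table 18 is introduced as giving "the expected power to demonstrate a reduction on 4 primary BoExps in smokers switching from CC to THS 2.2", at the same 80/40/40 allocation and one-sided 2.5% level. Its 50% column reads 96% (YVD-CS01-EU) and >99% (ZRHX-EX-01). SAP section 8, Table 13, repeats these values. Neither section gives 80% for the primary endpoints. In both, 80% appears only for the precision of the THS 2.2 to SA ratios, for CYP1A2 and for 11-DTX-B2.

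On what counts as success, Protocol section 12.4.1 says: "The study will be considered successful if the study demonstrates a 50% reduction or more for all four primary BoExp". The synopsis (Primary Endpoints, Evaluation Criterion), Protocol section 3.4.1 and SAP section 5.5.2 set the same rule. Protocol section 12.1.5 adds that "statistical significance is required for all primary endpoints in order to be able to make confirmatory claims about any of the endpoints", and SAP section 12.1.7 agrees.

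**The concern.** The synopsis and section 12.2 describe the same comparison, size, test and threshold, but they differ in two ways. The power is 80% in one place and 96% or more in the other. The event is any biomarker in one place and the four biomarkers in the other. The word *needed* adds a third difficulty: it presents 160 as the size at which the primary comparison just reaches 80%, which Table 18 contradicts.

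The synopsis is the short account of why 160 people are randomized and confined. A reader who relies on its Sample Size paragraph gets a power figure that the protocol does not derive anywhere, attached to an event that does not decide the trial.

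**Working it through.** **Inputs.** There are 80 THS 2.2 and 40 CC subjects (synopsis; section 12.2). The level is one-sided 2.5%. The threshold is a THS 2.2/CC ratio of 0.50. The scale follows section 12.4.4: "Analysis of BoExp will be conducted on the natural log scale". Mean ratios (MR) and CVs come from Protocol Tables 16 and 17.

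**Formulas.** SD = √ln(1 + CV²). Distance to the threshold d = ln(0.50/MR). SE = SD × √(1/80 + 1/40). Power is the noncentral t probability with 118 df and noncentrality d/SE.

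**Each biomarker at the 50% threshold**

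| Assumptions | Biomarker | MR (CV) | SD | d | d/SE | Power |
|---|---|---|---|---|---|---|
| YVD-CS01-EU | COHb | 0.40 (0.32) | 0.312 | 0.223 | 3.69 | 95.5% |
| | 3-HPMA | 0.30 (0.50) | 0.472 | 0.511 | 5.58 | 99.98% |
| | MHBMA | 0.15 (0.70) | 0.631 | 1.204 | 9.85 | ~100% |
| | S-PMA | 0.20 (0.70) | 0.631 | 0.916 | 7.49 | ~100% |
| ZRHX-EX-01 | COHb | 0.44 (0.14) | 0.139 | 0.128 | 4.74 | 99.7% |
| | 3-HPMA | 0.28 (0.20) | 0.198 | 0.580 | 15.1 | ~100% |
| | MHBMA | 0.11 (0.47) | 0.447 | 1.514 | 17.5 | ~100% |
| | S-PMA | 0.07 (0.50) | 0.472 | 1.966 | 21.5 | ~100% |

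**All four.** The product of the four powers is 95.5% (YVD-CS01-EU) and 99.7% (ZRHX-EX-01). The product assumes independence, but this hardly matters. Whatever the correlation, under YVD-CS01-EU the joint power cannot exceed that of COHb alone (95.55%) or fall below 100% − 4.45% − 0.02% = 95.53%.

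**Does this reproduce the plan's own figures?** For reductions of 50, 51, 52, 53, 54 and 55%, the YVD-CS01-EU joint power is 95.5, 91.4, 84.8, 75.2, 62.8 and 48.5%. Table 18 prints 96, 91, 85, 75, 63 and 48%, so the row agrees. For ZRHX-EX-01 at 50%, 99.7% agrees with the printed >99%.

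**Does any reading of the synopsis give 80%?**

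- At least one of the four: practically 100%.
- Each of the four: the lowest is COHb, at 95.5% or 99.7%.
- All four: 95.5% or 99.7%.

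Harsher variants of the YVD-CS01-EU case also stay above 80%: 87.3% with a Bonferroni level of 0.025/4 = 0.00625, 88.2% with 40 against 40, and 90.3% with 20% attrition (64 against 32).

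**A limit on the working.** Beyond the 50% column, the ZRHX-EX-01 row of Table 18 does not follow from the printed COHb CV of 0.14. At 51 to 55% that CV gives 97.7, 89.2, 67.9, 37.2 and 12.8%, against the printed >99, 96, 81, 48 and 16%. A CV of about 0.12 fits. The 50% column, the only one used here, is above 99% with either value.

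**The case against.** **80% may be meant as a floor, and *any* as each.** Both readings are possible in ordinary English. The trial does attain 80%, and more. But the sentence says the size is needed to attain 80%, not that it gives at least 80%. And if *any* means each, the weakest biomarker still has 95.5%. The objection softens the wording complaint but leaves the figure wrong.

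**The synopsis does not mislead about success.** This largely stands. A reader might infer from *any* that one biomarker is enough. The same synopsis, under its Evaluation Criterion, requires all four, so the documents do not support that inference. The fault is confined to the power sentence.

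**160 may rest on other targets.** This also stands. For the primary endpoints alone, 80% joint power would be reached with 50 THS 2.2 + 25 CC (81.4%, YVD-CS01-EU) or 30 + 15 (81.0%, ZRHX-EX-01, using the printed CV of 0.14). A reader might infer that 160 is oversized. But section 12.2 and SAP section 8 also state 80% power for an 11-DTX-B2 difference of 24.71 with SD 43.78. At 80/40 the noncentrality is 24.71/(43.78 × √(1/80 + 1/40)) = 2.91, and the power is 82%. At 50/25 it falls to 62%, and at 30/15 to 41%. The same sections promise THS 2.2 to SA confidence limits within 18% with 80% probability. For S-PMA (CV 0.42), the upper limit is 17.7% above the estimate at 80/40, 23% at 50/25 and 32% at 30/15. These targets nearly bind at the planned size, and withdrawn subjects are not replaced. If they drove the size, the synopsis attributes it to the wrong comparison.

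**Perhaps 80% belongs to a larger reduction.** Recalculation with the printed CVs puts 80% near a 52.5% reduction under both assumption sets. Table 18 does not support stating that: its ZRHX-EX-01 row prints 96% at 52% and 81% at 53%, which places 80% at about 53%.

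**Conclusion.** The concern holds as an internal inconsistency in the synopsis. The stated power is 80%. At the same size, level and threshold, the plan's own figures are 96% and >99%, which recalculate as 95.5% and 99.7% for all four biomarkers. The stated event, *any*, also differs from the all-four event that decides the trial.

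The result rests on the printed mean ratios and CVs, lognormal data, 80 against 40 evaluable subjects and a one-sided 2.5% test. It barely depends on correlation, because COHb determines the joint power.

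The error is in the conservative direction. A reader who sees two power figures might suspect an underpowered trial. On the documents' assumptions it is not one, and hypotheses, level, allocation, analysis and success rule are unaffected.

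**What to change.** Replace the synopsis sentence with: *160 subjects (80/40/40) give about 96% (YVD-CS01-EU assumptions) and >99% (ZRHX-EX-01 assumptions) power to show at least a 50% reduction in all four primary BoExp in THS 2.2 compared to CC, one-sided 2.5%.* Delete the statement that this size is needed to attain 80% power.

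Do not add a statement tying 80% to a 52.5% reduction, and do not present the smaller sizes as sufficient for the trial.

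The cost is one sentence, with figures already in Table 18. Design, conduct and analysis do not change.

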11-DTX-B2	11-dehydro-thromboxane B2
ADL	Activities of daily living
AE	Adverse event
ALT	Alanine aminotransferase
ANCOVA	Analysis of covariance
AP	Alkaline phosphatase
AST	Aspartate aminotransferase
ATC	Anatomical Therapeutic and Chemical (WHO drug classification index)

Confidentiality statement: Data and information contained in this document are considered to constitute trade secrets and confidential commercial information, and the legal protections provided to such trade secrets and confidential information are hereby claimed under the provisions of applicable law. No part of this document may be publicly disclosed without the written consent of Philip Morris Products S.A.

ATS	American Thoracic Society
B	Blood
BMI	Body mass index
BoExp	Biomarker(s) of exposure
CAF	Caffeine
CC	Conventional cigarette(s)
CD	Compact Disc
CDISC	Clinical data interchange standards consortium
CEMA	2-cyanoethylmercapturic acid
CI	Confidence interval
CO	Carbon monoxide
COHb	Carboxyhemoglobin
COPD	Chronic obstructive pulmonary disease
CRA	Clinical Research Associate
CRO	Contract Research Organization
CSR	Clinical Study Report
CTCAE	Common Terminology Criteria for Adverse Event and Common Toxicity Criteria
CTMS	Clinical Trial Management System
CV	Coefficients of variation

Confidentiality statement: Data and information contained in this document are considered to constitute trade secrets and confidential commercial information, and the legal protections provided to such trade secrets and confidential information are hereby claimed under the provisions of applicable law. No part of this document may be publicly disclosed without the written consent of Philip Morris Products S.A.

CVD	Cardiovascular Disease
CYP1A2	Cytochrome P450 1A2
CYP2A6	Cytochrome P450 2A6
DMP	Data management plan
ECG	Electrocardiogram
eCRF	Electronic Case Report Form
EHCSS	Electrically heated cigarette smoking system
EOS	End of Study Visit
ERS	European Respiratory Society
FAS	Full analysis set
FDA	Food and Drug Administration
FEV ₁	Forced expiratory volume in 1 second
FSH	Follicle stimulating hormone
FTND	Fagerström Test for Nicotine Dependence
FVC	Forced vital capacity
GCP	Good Clinical Practice
Hb	Hemoglobin
HbA1c	Hemoglobin A1c
HbsAg	Hepatitis B surface antigen
Hct	Hematocrit

Confidentiality statement: Data and information contained in this document are considered to constitute trade secrets and confidential commercial information, and the legal protections provided to such trade secrets and confidential information are hereby claimed under the provisions of applicable law. No part of this document may be publicly disclosed without the written consent of Philip Morris Products S.A.

HCV	Hepatitis C virus
HDL	High density lipoprotein
HEMA	2-hydroxyethyl mercapturic acid
HIV	Human immunodeficiency virus
HMPMA	3-hydroxy-1-methylpropylmercapturic acid
HPHCs	Harmful or potentially harmful constituents
HST	Human smoking topography
IB	Investigator's Brochure
ICF	Informed consent form
ICH	International Conference on Harmonization
IEC	Independent Ethics Committee
IOM	Institute of Medicine
IP	Investigational Product
IRB	Institutional Review Board
ISO	International Organization for Standardization
IWRS	Interactive Web and Voice Response System
LDH	Lactic dehydrogenase
LDL	Low density lipoprotein
LLN	Lower limit of the normal range
LOCF	Last observation carried forward
MCEQ	Modified Cigarette Evaluation Questionnaire

Confidentiality statement: Data and information contained in this document are considered to constitute trade secrets and confidential commercial information, and the legal protections provided to such trade secrets and confidential information are hereby claimed under the provisions of applicable law. No part of this document may be publicly disclosed without the written consent of Philip Morris Products S.A.

MCH	Mean corpuscular hemoglobin
MCHC	Mean corpuscular hemoglobin concentration
MCV	Mean corpuscular volume
MedDRA	Medical Dictionary for Regulatory Activities
MHBMA	Monohydroxybutenyl mercapturic acid
miRNA	Micro-RNA
MNWS	Minnesota Nicotine Withdrawal Scale (revised version)
MR	Mean ratios
mRNA	Messenger-RNA
M RTP	Modified risk tobacco product
NEQ	Nicotine equivalents
NNAL	4-(methylnitrosamino)-1-(3-pyridyl)-1-butanol
NNAL-glucuronides	[4-(methylnitrosamino)-1-(3-pyridyl) but-1-yl]- β -N-D-glucosiduronic acid and [4-(methylnitrosamino)-1-(3-pyridyl) but-1-yl]- β -O-D-glucosiduronic acid
NNK	4-(methylnitrosamino)-1-(3-pyridyl)-1-butanone
NNN	N-nitrosornicotine
NRT	Nicotine Replacement Therapy
NSAID	Nonsteroidal Anti-inflammatory Drugs
o-tol	o-toluidine
PI	Principal Investigator
PK	Pharmacokinetic(s)

Confidentiality statement: Data and information contained in this document are considered to constitute trade secrets and confidential commercial information, and the legal protections provided to such trade secrets and confidential information are hereby claimed under the provisions of applicable law. No part of this document may be publicly disclosed without the written consent of Philip Morris Products S.A.

PMI	Philip Morris International
PX	Paraxanthine
QSU-brief	Questionnaire of Smoking Urges (brief version)
RBC	Red blood cell (count)
RNA	Ribonucleic acid
SA	Smoking abstinence
SAE	Serious adverse event
SAP	Statistical analysis plan
SD	Standard deviation
SHM	Sample handling manual
SOP	Standard Operating Procedure
S-PMA	S-phenylmercapturic acid
THS	Tobacco heating system
U	Urine
█	█
ULN	Upper limit of the normal range
VAS	Visual analogue scale
WBC	White blood cell (count)
WHO	World Health Organization
WHO-DDE	WHO Drug Dictionary Enhanced

Confidentiality statement: Data and information contained in this document are considered to constitute trade secrets and confidential commercial information, and the legal protections provided to such trade secrets and confidential information are hereby claimed under the provisions of applicable law. No part of this document may be publicly disclosed without the written consent of Philip Morris Products S.A.

Definition of Terms

The following special terms are used in this protocol:

Baseline period	06:30 AM at Day -1 until 06:29 AM of Day 1.
Charger	The function of the Charger (Model 4) is to recharge the Holder after use. It contains a battery with sufficient capacity to recharge the Holder approximately 20 times. It is a convenient size to carry around, and can itself be recharged from a mains power source.
CC	The term ‘conventional cigarette’ refers to manufactured and commercially available cigarettes and excludes hand-rolled cigarettes, cigars, pipes, bidis, and other nicotine-containing products.
CC incompatible with HST device	All CCs that are incompatible with the HST device (e.g. slim CC).
Day of Discharge	Day 6.
End of the study	End of Study is defined as the last day of the 7 day safety follow-up subsequent to discharge from the unit.
Enrolment	On Day -2 for eligible subjects after all applicable inclusion and exclusion criteria have been satisfactorily met and the subject is willing and ready to use THS 2.2 (the test of THS 2.2 is the last assessment prior to enrolment).
Exposure period	06:30 of Day 1 until 11:00 PM of Day 5.
Investigator	Principal Investigator or sub-Investigator
Randomization	Assignment of the subject randomization number in the Interactive Web and Voice Response System. This can be done any time on Day 0, however subjects are not to be informed of their randomization group and number prior Day 1.
Run-in period	Admission to site until 06:30 of Day -1.
Safety follow-up	After the time of discharge, a 7-day safety follow-up will be done for the recording of spontaneously reported new AEs/SAEs and the active follow-up of ongoing AEs/SAEs. In general, any AE will be followed-up until resolved, stabilized i.e., no worsening of the event, or a plausible explanation for the event has been found.

Confidentiality statement: Data and information contained in this document are considered to constitute trade secrets and confidential commercial information, and the legal protections provided to such trade secrets and confidential information are hereby claimed under the provisions of applicable law. No part of this document may be publicly disclosed without the written consent of Philip Morris Products S.A.

Screening failure	Subjects who do not meet the entry criteria from ICF/ signature to the time of enrolment will be considered a screening failure and will be replaced by other subjects.
Time of Discharge	The time of day the subject is discharged on Day of Discharge.
THS Tobacco Stick Holder (Holder)	The function of the Holder (Model 4.2) is to heat the Tobacco Stick, delivering an aerosol to the user. The electrical heating is powered from an internal battery which delivers power for about 6 minutes (allowing complete use of a single Tobacco Stick).
Tobacco Heating Device	The Device comprises everything in THS 2.2, except the Tobacco Stick
Tobacco Heating System 2.2 (THS 2.2)	THS 2.2 comprises the following components: Tobacco Stick, Holder, Charger, a Cleaning Tool, a mains power supply, and a USB cable.
THS Tobacco Stick (Tobacco Stick)	The THS Tobacco Stick (Tobacco Stick) (product code C3) contains tobacco which, when heated, generates an aerosol. It is custom-designed to be used with the Holder.

